3.0 DATA MANAGEMENT PROCEDURES

This protocol will utilize a centralized Data and Statistics Center (DSC). A web-based distributed data entry model will be implemented. This electronic data capture system (Advantage eClinical) will be developed to ensure that guidelines and regulations surrounding the use of computerized systems in clinical trials are upheld.

4.0 DATA AND STATISTICS CENTER RESPONSIBILITIES

The DSC will: 1) develop and apply data management procedures to ensure the collection of accurate and good-quality data, 2) provide source documents and electronic Case Report Forms (eCRFs) for the collection of all data required by the study, 3) develop data dictionaries for each eCRF that will comprehensively define each data element, 4) prepare instructions for the use of Advantage eClinical and for the completion of eCRFs, 5) conduct ongoing monitoring and quality assurance activities on study data collected from all participating sites, and 6) perform data cleaning activities prior to the final study database lock for assessments collected in Advantage eClinical.

A. DATA COLLECTION AND ENTRY

Data will be collected at the study sites on source documents and entered by the site into eCRFs in Advantage eClinical or will be collected via direct entry into the eCRF. In the event that Advantage eClinical is not available, the DSC will provide the sites with a final set of guided source documents with instructions for completion. Data will be entered into Advantage eClinical in accordance with the instructions provided during protocol-specific training and guidelines established by the DSC. Data entry into the eCRFs will be performed by authorized individuals who have satisfactorily completed the relevant training. Selected source documents and eCRFs may also require the investigator's signature (wet or electronic). In some situations, data collected on source documents will not be entered into Advantage eClinical, but when it is entered, it will follow the guidelines stated above.

The Principal Investigator at the site is responsible for maintaining accurate, complete and up-to-date research records. In addition, the Principal Investigator is responsible for ensuring the timely completion of eCRFs for each research participant.

B. DATA MONITORING, CLEANING AND EDITING

eCRFs will be monitored for completeness and accuracy throughout the study. Dynamic reports listing missing values and missing forms are available to sites at all times in Advantage eClinical. These reports will be monitored regularly by the DSC. In addition, the DSC will identify inconsistencies within eCRFs and between eCRFs and post queries in Advantage eClinical on a scheduled basis. Sites will resolve data queries by entering all corrections and changes directly into Advantage eClinical or by verifying the data are correct as is.

As described above, the CCC will conduct regular monitoring visits, during which audits

comparing source documents to the data entered on the eCRF will be performed. Any discrepancies identified between the source document and the eCRF will be corrected by the site.

Trial progress and data status reports, which provide information on items such as recruitment, availability of primary outcome data, treatment exposure, attendance at long term follow-up visits, regulatory status, and data quality, will be generated daily and posted to a secure website. These reports are available to the site staff, local Node staff, the Lead Investigator, the coordinating centers, and NIDA CCTN, to monitor each site's progress on the study.

C. DATABASE LOCK AND TRANSFER

Study participant research data, which is for purposes of statistical analysis and scientific reporting, will be transmitted to and stored at the DSC. Individual participants and their research data will be identified by a unique study identification number; further, some identifiable data may be collected in eClinical. The study data entry and study management systems used by clinical sites and by DSC staff will be secured and password protected in compliance with regulatory standards.

At the conclusion of data collection for the study, the DSC will perform final data cleaning activities and will "lock" the study database from further modification. The final raw datasets will be transferred to the Lead Investigator or designee. De-identified versions of these datasets will also be provided to the NIDA CCTN-designated party for storage and archiving. These datasets may be posted on the NIDA Data Share website.

Reference: <http://grants.nih.gov/grants/guide/notice-files/not98-084.html>

SOWS	Subjective Opiate Withdrawal Scale
SP	Standard Procedure
SW	Stepped-Wedge
TAU	Treatment as Usual
TLFB	Timeline Followback
TSE	Targeted Safety Event
UDS	Urine Drug Screen
VAS	Visual Analog Scale
XR-NTX	Extended-Release Naltrexone (Vivitrol®)

LIST OF eCRFs

AAS	Adult ADHD Self-Report Screening Scale for DSM-5
AD1	Adverse Event
AD2	Serious Adverse Event Summary
AD3	Serious Adverse Event Medical
ASU	Alcohol and Substance Use
C97	Critical Action Checklist
CMX	Concomitant Medications
COW	Clinical Opioid Withdrawal Scale
CUT	Clinic Urine Toxicology
CVD	COVID-19 Impact Assessment
D97	Study Demographics (RA/RC Administered)
DEM	Demographics
DMA	Daily Medication Administration Log
DSM	DSM-5 Checklist
DTH	Death Form
EIP	End of Induction Survey
ENRA	Enrollment into Segment A
ENRB	Enrollment into Segment B
ENRC	Enrollment into Segment C
ENRD	Enrollment into Segment D
ENRE	Enrollment into Segment E
EO2	End of Medication (Self-Reported)
EOI	End of Induction
EOM	End of Medication
FAM	Family Origin
FC1	Pre-Implementation Fidelity to Implementation Checklist
FC2	Post-Implementation Fidelity to Implementation Checklist
FND	Fagerström Test for Nicotine Dependence
FOO	Fatal Opioid Overdose
GA7	Generalized Anxiety Disorder
GEN	Genetics
HEP	Self-Report of Hepatitis Testing and Treatment
HIV	Self-Report of HIV Testing
INA	Injection Site Abnormality
INB	Induction Buprenorphine
INN	XR-NTX Administration
LDN	Low Dose Naltrexone Titration
LIF	Locator Information Form

M97	Timeline Followback Medications
MGT	Medical Management
MHA	Mental Health Follow-up Assessment
MHX	Medical Psychiatric History
MJA	Cannabis Use Assessment
MTV	Motivation Scale
NM2	Non-Medical and Other Services - Page 2
NMS	Non-Medical and Other Services
OCI	Opioid Craving Scale
OCO	Opioid Craving Scale
ODQ	Overdose Questionnaire
OES	Opioid Effect Scale
OLC	Organization Level Clinical Implementation
OR1	Pre-Implementation Organizational Readiness to Change Assessment
OR2	Post-Implementation Organizational Readiness to Change Assessment
PBC	Pregnancy and Birth Control Assessment
PCL	PTSD Checklist for DSM-5
PDA	Panic Disorder Assessment
PHQ	Patient Health Questionnaire (PHQ-9)
PO1	Pregnancy Outcome 1
PO2	Pregnancy Outcome 2
PO3	Pregnancy Outcome 3
PO4	Pregnancy Outcome 4
PRG	Confirmed Pregnancy and Outcome
PRO	PROMIS
PSA	Prisoner Status Assessment
PST	Psychosocial Treatment
QLP	Quality of Life
S97	Additional Demographics
SBW	The Subjective Opiate Withdrawal Scale
STC	Study Completion
T97	Timeline Followback
TAP	TLFB Assessment Period
TS5	Treatment Satisfaction Survey
TSE	Targeted Safety Event
TUH	Tobacco Use History
UDS	Urine Drug Screen
V97	Missed Visit and Visit Documentation

1.0 INTRODUCTION

The Statistical Analysis Plan (SAP) for CTN-0097 Surmounting Withdrawal to Initiate Fast Treatment with Naltrexone: Improving the Real-World Effectiveness of Injection Naltrexone for Opioid Use Disorder (SWIFT) expands upon the statistical information presented in the protocol and describes all planned analyses for the primary, secondary, exploratory, implementation, and safety outcome measures occurring after data lock. The Clinical Trial Network (CTN)'s Data and Statistics Center (DSC) will conduct the analyses for the Final Study Report (FSR) as listed in Table 1 below and the Lead Node (LN) will conduct the analyses as noted.

Table 1: Analysis Responsibilities		
Content	Section Number	Responsible for Analysis
Participant Enrollment, Disposition, and Follow-up	4.0	DSC
Participant Baseline Characteristics	5.0	DSC
Medications Administered During Induction Phase	6.0	DSC
Analyses of Treatment Exposure	7.0	DSC
Analyses of Primary Outcome	8.2	DSC
Supportive Analyses of Primary Outcome ¹	8.3	DSC/LN
Analyses of the Key Secondary Outcome Measures	8.5	DSC
Analyses of the Other Secondary Outcome Measures	8.5	LN
Analyses of the Exploratory Outcome Measures	8.6	LN
Analyses of the Implementation Outcomes	9.0	LN
Safety Outcomes	10.0	DSC
Data Quality	14.0	DSC

¹ Details will be provided in Section 8.3.

2.0 SUMMARY OF STUDY DESIGN AND PROCEDURES

2.1 Study Objectives

2.1.1 Primary Objective

The primary goal of the study is to determine whether the Rapid Procedure (RP) method of initiating treatment with XR-NTX is non-inferior to the Standard Procedure (SP) method recommended in the XR-NTX Prescribing Information. The primary outcome measure is a dichotomous measure of treatment initiation success defined as receipt of the first injection of XR-NTX while inpatient on a detoxification or residential rehabilitation unit. The hypothesis is that the RP will be non-inferior to SP in terms of proportion of successful initiations of XR-NTX.

2.1.2 Secondary Objectives

The key secondary objective is to summarize the below outcome to confirm expected characteristics of the RP compared to SP:

1. Time to receipt of first injection of XR-NTX from day of admission for participants that receive first injection of XR-NTX while on the unit.

Additional key secondary objectives are to compare the below outcomes of RP versus SP for all enrolled participants, intent-to-treat (ITT) population.

2. Craving for opioids measured by Visual Analog Scales (VAS).
3. Opioid withdrawal symptoms as measured by the Subjective Opioid Withdrawal Scale (SOWS) and the Clinical Opiate Withdrawal Scale (COWS).
4. Safety, as measured by overdose questionnaire, targeted safety events and serious adverse events.

Other secondary objectives are to compare the below outcomes of RP vs. SP for participants who receive the first injection while on the unit.

5. Retention in the trial to receive the second and the third XR-NTX injections.
6. Craving for opioids measured by Visual Analog Scales.
7. Opioid withdrawal symptoms following XR-NTX injection as measured by the Subjective Opioid Withdrawal Scale.
8. Safety, as measured by overdose questionnaire, targeted safety events and serious adverse events.
9. Opioid abstinence, as measured by the Timeline Followback (TLFB) (self-report days using opioids) and proportion of opioid-positive urine tests (UDS).

2.1.3 Exploratory Objectives

Exploratory objectives include:

1. Explore baseline demographic and clinical features (e.g., the primary opioid of dependence (heroin/fentanyl vs. prescription opioid)) as: a) predictors of induction success, secondary outcomes and retention during the trial (main effect of predictors), and b) as moderators of differential treatment effect (moderator by treatment interaction).
2. Compare duration of treatment on the unit and the associated costs from the time when detoxification is initiated to the time that XR-NTX is administered to permit analyses of economic costs and benefits of the two induction procedures.
3. Compare RP versus SP for all enrolled participants in terms of time from day of admission to XR-NTX initiation failure (day of discontinuation of detoxification period that resulted in failure to receive first XR-NTX) and reasons for failure.
4. Compare RP versus SP for all enrolled participants in terms of other depressive, anxiety, and subacute withdrawal symptoms as measured by the Patient Health Questionnaire-9 (PHQ-9) and General Anxiety Disorder-7 (GAD-7).
5. Compare RP versus SP use of alcohol and other drugs of abuse (e.g., cocaine, other stimulants, cannabis, benzodiazepines), by self-report and urine drug screens for all enrolled participants.

6. Explore engagement with medical visits and therapy (based on Medical Management Log, Psychosocial Log, XR-NTX Administration Form, TLFB).
7. Compare RP versus SP for the percentage of patients inducted onto any MOUD (XR-NTX, buprenorphine, or methadone, as measured by TLFB for MOUD), both before discharge from inpatient unit and after discharge from inpatient unit).
8. Investigate the percentage of induction failure participants that receive XR-NTX during the course of the study overall and for each induction procedure as measured by patient self-report on TLFB).
9. Compare RP versus SP for percentage of participants inducted on XR-NTX (during both induction and post-induction phases of the trial).

2.1.4 Implementation Objectives

[figure not shown]
The objective of the implementation component of the study is to understand facilitators and barriers to implementation of Rapid initiation of XR-NTX and to iteratively develop an implementation facilitation manual which can be used to disseminate XR-NTX initiation methods across the treatment system. Measurement will be grounded in the CFIR (Damschroder and Hagedorn, 2011) and will assess intervention characteristics (provider survey), inner setting factors (e.g., readiness, clinical leadership structure, resources; survey and environmental scan), individual provider characteristics (provider survey), and implementation process through fidelity measures. Following each stepped wedge, this information will be integrated into the IF manual (by adding new information and/or making modifications to existing information) to improve the procedures. The ultimate goal will be to produce a high quality IF manual at the conclusion of trial which could facilitate widespread implementation of XR-NTX induction across community-based treatment settings, as well as be tested within its own right in a larger implementation-focused trial.

2.2 Study Design and Procedures

2.2.1 Study Design

This is a six-center, stepped-wedge, cluster randomized trial comparing effectiveness and safety of Rapid (5-7 days) versus Standard (13 days) XR-NTX induction procedure (RP vs. SP). The study will proceed in five steps, with each step lasting 14 weeks, for the total of 70 weeks of the study (Table 2). A total of 450 participants (15 per site per step) eligible for and seeking treatment for opioid disorder with XR-NTX and consenting to research assessments during their course of XR-NTX treatment are planned to be enrolled in the study. Enrolled participants will receive the naltrexone initiation regimen being offered at the site at the time of admission, either SP or RP depending on the random assignment as per study design. At the beginning of each step a randomly selected site will begin implementing RP and will continue to offer it for the remainder of the trial, according to the optimized stepped-wedge study design (Thompson et al., 2017). Note the first randomized site will offer only RP whereas the last remaining site will offer only SP for the entire duration of the trial. After sites transition to RP, this will be the only regimen available for patients interested in participating in the research study (i.e., SP will no longer be offered as a part of the study). Before each stepped wedge of the study, an 8-week pre-implementation or preparation phase will occur for each site randomized to RP. During the implementation phase of RP, the implementation team will meet routinely to review the implementation process and identify modifiable barriers or facilitators to facilitate RP implementation. After each stepped wedge, the study team with expertise in implementation will meet to review identified barriers and facilitators to implementing the RP intervention and modify or adapt the RP Implement Facilitation package accordingly. Site level and provider/staff level surveys will be completed before and after implementation of RP.

Table 2: Schematic of study design with six study sites and five steps, each lasting 14 weeks

2.2.2 Study Assessments

All assessments and corresponding case report forms by study phase and study visit are described below.

During pre-screening (Day -7 up to Day 3 of admission), potential participants will be assessed for basic eligibility to move forward in the study. Patients that meet pre-screening basic eligibility criteria will be asked to sign the informed consent (IC) no later than Day 4 of admission. Patients that sign the IC enter the screening phase and are assessed for eligibility to enroll in the study no later than Day 4 of admission. The following assessments are performed during screening: Demographics (DEM), Prisoner Status Assessment (PSA), Locator Information Form (LIF), Concomitant Medications (CMX), Medical Psychiatric History (MHX), DSM-5 Checklist (DSM), Pregnancy and Birth Control Assessment (PBC), and Urine Drug Screen (UDS).

Following the final confirmation of eligibility for study enrollment participants complete baseline assessments during Days 1-4: Study Demographics (D97), Genetics (GEN), Family Origin (FAM), Alcohol and Substance use (ASU), Non-Medical and other Services (NMS/NM2), Timeline Follow-back – Substance and MOUD (TAP/T97/M97), Concomitant Medications (CMX), Pregnancy and Birth Control Assessment (PBC), Urine Drug Screen (UDS), Daily Medication Administration Log (DMA), Clinical Opiate Withdrawal Scale (COW), and Medical Management (MGT). In addition, the following self-reported baseline assessments will be collected from participants: Additional Demographics (S97), Opioid Craving Scale Inpatient (OCI), Overdose Questionnaire (ODQ), The Subjective Opioid Withdrawal Scale (SBW), Cannabis Use Assessment (MJA), Tobacco Use History (TUH), Fagerström Test for Nicotine Dependence (FND), Motivation Scale (MTV), Quality of Life (QLP), PROMIS (PRO), Panic Disorder Assessment (PDA), Generalized Anxiety Disorder (GA7), PTSD Checklist for DSM-5 (PCL), Patient Health Questionnaire-9 (PHQ), Mental Health Assessment (MHA), Adult ADHD Self-Report Screening Scale for DSM-5 (AAS), Self-Report of Hepatitis Testing and Treatment (HEP), Self-Report of HIV Testing (HIV) and COVID-19 Impact Assessment (CVD).

Induction Phase Assessments (Day 1 – Day 30)

The induction phase for enrolled participants (within both RP and SP) begins with day of admission (induction phase Day 1) and ends on the day of XR-NTX receipt or day of failure of the induction protocol. The maximum length of the induction phase is 30 days. For participants who leave the unit prior to Day 30, the date of leaving the unit without a medication would be equivalent to date of failure as recorded on the EOI form per the CRF manual. Daily and weekly assessments will be conducted during the induction phase as follows:

- Daily assessments (DMA, Low Dose Naltrexone Titration [LDN] for the Rapid Protocol only, COW, OCI, SBW, Psychosocial and Medical Treatment Participation log [PST]).

- Weekly assessments (GA7, PHQ).
- Assessments collected prior to first XR-NTX injection include UDS (all participants) and PBC (females only).
- Data will be collected retrospectively starting with induction phase Day 1, using medication flowsheets and EMR abstraction (performed and confirmed by study staff). The following assessments may be retrospectively collected/abstracted: DMA, COW, UDS and PBC.
- End of Induction (EOI) and End of Induction Survey (EIP) are collected at the end of the induction phase regardless of whether the participant receives their first dose of XR-NTX on the unit, if the participant terminates the induction protocol early, or if they exceed the maximum window allowed for the induction phase.

Post-Induction Phase Assessments (Week 1 – Week 8)

The post-induction phase will begin the day after receiving XR-NTX injection or the day after failure of the induction protocol (Day 1 post-induction). During the 8-week post-induction phase, participants will receive medication management visits per the site's standard clinical practice, plus an additional two XR-NTX injections, expected at four and eight weeks after the first XR-NTX injection, along with other psychosocial treatment as per the standard of care provided by each site. The following assessments will be conducted during post-induction phase at Weeks 1, 2, 3, 4, 6 and 8: Missed Visit and Visit Documentation (V97), TAP/T97/M97, MGT, OCO, ODQ, SBW, OES, GA7, PHQ, PST. UDS (all participants) and PBC (females only) will be assessed prior to each XR-NTX injection. Additional assessments will be performed at week 3 (PSA) and week 4 and 8 (INN, NMS/NM2).

Note that participants who fail the induction phase will still be enrolled into the post-induction phase but only assessed at Weeks 4 and 8. Participants who discontinue XR-NTX early (i.e. do not receive both injections) will complete the Early End of Medication Visit and the following assessments will be performed: V97, CMX, MGT, End of Medication (EOM), and End of Medication – Self-Reported (EO2).

Other assessments will be performed as needed: Injection Site Abnormality (INA), Mental Health Follow-Up Assessment (MHA), Study Completion (STC).

In addition to the above assessments, the study will collect data on implementation facilitation outcomes: Organization Level Clinical Implementation (OLC) at the start of each step at all sites, Pre/Post Organizational Readiness to Change Assessment (ORCA) (OR1/OR2) prior to and at the end of RP implementation step at the randomized site, Pre/Post Fidelity to Implementation Checklist (FC1/FC2) at the start and end of RP implementation step at the randomized site. OR1/OR2 collect provider/staff level data whereas OLC and FC1/FC2 collect site level data.

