10.5 Post-Induction Treatment (Phase 3)

Following the administration of the first XR-NTX dose or induction failure, participants will be encouraged to continue follow-up treatment per standard clinical practice. The sites should provide outpatient care as clinically appropriate and are recommended to provide participants with at least weekly clinic visits during the first month of treatment then biweekly visits during the second month. Participants will also complete research ratings, including self-report of withdrawal, mood, and drug use as noted in Section 12. The participant provides a urine sample at each injection visit for an onsite toxicology testing.

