12.7.6 Table 7: Study Assessments

	Consent	Screening	Baseline	Inpatient Induction Phase		Post-Induction Phase						End of Medication Treatment
				Rapid Procedure	Standard Procedure	1	2	3	4	5	6	
Visit #				1	2	3	4	5	6	8		
Week												
Time				IND-RP	IND-SP	P6	P13	P20	P27	P41	P55	Varies
General Anxiety Disorder-7			X	X ²	X ²	X	X	X	X	X	X	
HIV and Hepatitis Assessments			X									
Urine Pregnancy and Birth Control Assessment		X		X ³	X ³				X ³		X ³	
Daily Medication Administration Log			X	X	X							
Concomitant Medications		X				X	X	X	X	X	X	X
AEs & SAEs	X	X	X	X	X	X	X	X	X	X	X	X
Opioid Overdose Questionnaire			X			X	X	X	X	X	X	
Medication Injection Site Abnormality Log				^	^	^	^	^	^	^	^	^
Death Form		^	^	^	^	^	^	^	^	^	^	^
Saliva Sample (Genetic Sample)			X									
Family Origin Assessment			X									
TREATMENT SCHEDULE												
Induction Buprenorphine				X	X							
Naltrexone Titration				X								
XR-NTX Administration				X	X				X		X	

	Consent	Screening	Baseline	Inpatient Induction Phase		Post-Induction Phase						End of Medication Treatment
				Rapid Procedure	Standard Procedure	1	2	3	4	5	6	
Visit #				1	2	3	4	5	6	8		
Week				1	2	3	4	6	8			
Time				IND-RP	IND-SP	P6	P13	P20	P27	P41	P55	Varies
ADHERENCE												
Medical Management Log				X	X	X	X	X	X	X	X	X
Psychosocial Log				X	X	X	X	X	X	X	X	
OUTCOME												
Timeline Followback – Substance Use			X			X	X	X	X	X	X	
Timeline Followback – MOUD			X			X	X	X	X	X	X	
Urine Drug Screen		X		X ³	X ³				X ³		X ³	
PROMIS			X						X		X	
VAS Opioid Craving			X	X ⁴	X ⁴	X	X	X	X	X	X	
VAS Opioid Effect						^	^	^	^	^	^	
Patient Health Questionnaire-9			X	X ²	X ²	X	X	X	X	X	X	
Mental Health Assessment			^			^	^	^	^	^	^	
Subjective Opioid Withdrawal Scale			X	X ⁴	X ⁴	X	X	X	X	X	X	
Clinical Opioid Withdrawal Scale			X	X ⁵	X ⁵							
Non-Medical and Other Services			X						X		X	

X¹ = Includes ASU, TUH, QLP assessments

X² = repeat weekly during inpatient induction phase

X³ = before each XR-NTX injection

X⁴ = repeat each inpatient study day

X⁵ = repeat daily, as many times as clinically appropriate

^ = As Needed

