16.9 Missing Data and Dropouts

The primary outcome, whether or not a participant receives the XR-NTX while inpatient, is not expected to have missing data. Other outcome variables (opioid and other substance use over time, craving, mood, etc.) will have missing data due to missed visits and dropout from treatment and from study participation. The generalized linear model, or mixed effects model framework that will be used for analyses, works with what data are gathered, and assumes missing data are missing at random. For selected secondary outcome analyses, sensitivity analyses will be considered to examine the stability of estimated treatment effects in the face of departures from the assumption of missing at random.

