Other secondary objectives to be analyzed by the LN are to compare the below outcomes of RP vs. SP for participants who receive the first injection while on the unit (Inducted Population):

- Opioid abstinence, as measured weekly by the Timeline Followback (TLFB) (self-report days using opioids) during the eight weeks of post-induction and proportion of opioid-positive urine tests as captured on the Urine Drug Screen (UDS) form at post-induction 4 week and 8 week visits.
- In addition, craving for opioids, opioid withdrawal symptoms, and safety events will be assessed in the inducted population similar to the key secondary outcomes.

Table 5: Secondary Clinical Outcomes, Outcome Measures and Hypotheses		
Outcome	Outcome Measure	Hypothesis
Time from admission to first XR-NTX injection	Days to first XR-NTX injection	Participants in the RP will receive their first injection significantly faster than those in the SP. Significance/Rationale: The RP decreases the time to the first injection (which has a potential to decrease costs and staff burden).
Opioid craving (VAS) over time	Mean for opioid craving measured by VAS daily during days leading to the first XR-NTX injection, and during post-induction Weeks 1-8	Participants in RP and SP will have comparable intensity of craving during 1) the inpatient treatment period, and 2) during the first week after the first XR-NTX injection. Significance/Rationale: Earlier trial showed comparable craving severity in both procedures (Sullivan et al. , 2017).
Opioid withdrawal (SOWS and COWS) over time	Mean for opioid withdrawal measured by SOWS and COWS score, daily (starting with day of admission) during days leading to the first XR-NTX injection and during post-induction Weeks 1-8	Participants in RP and SP will have comparable severity of opioid withdrawal during: 1) the inpatient treatment period, and 2) during the first four weeks after the first XR-NTX injection. Significance/Rationale: Earlier trial showed comparable withdrawal severity in both procedures (Sullivan et al. , 2017).

Table 5: Secondary Clinical Outcomes, Outcome Measures and Hypotheses

Outcome	Outcome Measure	Hypothesis

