8.6 Definition of the Exploratory Outcome Measures

Exploratory objectives include:

1. Explore baseline demographic and clinical features (e.g., the primary opioid of dependence (heroin/fentanyl vs. prescription opioid)) as: a) predictors of induction success, secondary outcomes and retention during the trial (main effect of predictors), and b) as moderators of differential treatment effect (moderator by treatment interaction).
2. Compare duration of inpatient treatment and the associated costs from the time when detoxification is initiated to the time that XR-NTX is administered to permit analyses of economic costs and benefits of the two induction procedures. Also compare duration of inpatient treatment for all patients regardless of whether XR-NTX was initiated, across RP and SP for ITT population. Participants who failed induction will be evaluated to see if they received any other MOUD.
3. Compare RP versus SP for all enrolled participants in terms of time from day of admission to XR-NTX initiation failure (day of discontinuation of detoxification period that resulted in failure to receive first XR-NTX) and reasons for failure.
4. Compare RP versus SP for all enrolled participants in terms of other depressive, anxiety, and subacute withdrawal symptoms as measured by the Patient Health Questionnaire-9 (PHQ-9) and General Anxiety Disorder-7 (GAD-7).
5. Compare RP versus SP use of alcohol and other drugs of abuse (e.g., cocaine, other stimulants, cannabis, benzodiazepines), by self-report and urine drug screens for all enrolled participants.
6. Explore engagement with medical visits and therapy (based on Medical Management Log, Psychosocial Log, XR-NTX Administration Form, TLFB).
7. Compare RP versus SP for all enrolled participants in terms of use of MOUD as measured by patient self-report on Timeline Followback (TLFB).
8. Investigate the percentage of induction failure participants that receive XR-NTX during the course of the study overall and for each induction procedure as measured by patient self-report on Timeline Followback.
9. Compare RP versus SP for percentage of participants inducted on XR-NTX (during both induction and post-induction phases of the trial).

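### Follow-up urine drug screens are scheduled only before an XR-NTX injection, while the urine outcomes are defined by visit or promised for everyone enrolled

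*SAP*

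**What the plan says.** Three places tie follow-up urine drug screens (UDS) to an injection:

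- SAP 2.2.2 lists the forms completed at Weeks 1, 2, 3, 4, 6 and 8 without UDS, then adds separately that "UDS (all participants) and PBC (females only) will be assessed prior to each XR-NTX injection".
- Protocol Table 7 marks UDS at Weeks 4 and 8 with footnote 3, "before each XR-NTX injection". The UDS cell for the End of Medication Treatment visit is empty.
- Protocol 10.5: "The participant provides a urine sample at each injection visit for an onsite toxicology testing".

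Other places define the outcomes without that condition:

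- SAP 8.4 uses the "proportion of opioid-positive urine tests as captured on the Urine Drug Screen (UDS) form at post-induction 4 week and 8 week visits", in the Inducted Population. Protocol Table 3 and SAP Table 5 also place the screens at Weeks 4 and 8.
- Exploratory objective 5 (Protocol 5.3; SAP 2.1.3 and 8.6) compares alcohol and other drug use "by self-report and urine drug screens for all enrolled participants".

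Induction failures are followed at Weeks 4 and 8 only (SAP 2.2.2). Protocol 6.1.4.2 wants to know by then whether they have relapsed. For outcomes other than the primary, the modelling framework in Protocol 16.9 "assumes missing data are missing at random".

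**The concern.** If urine is taken only when an injection is about to be given, having a urine result depends on still being on XR-NTX. Protocol 10.5.6 allows a missed injection to be rescheduled only if the participant has not relapsed and become dependent again, and Protocol 10.5.7 lists relapse among the reasons to stop. Opioid use can therefore end the injections and, with them, the urine screens. A missing-at-random analysis of the remaining urines does not deal with that unless self-report or other modelled data explain the missingness.

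At stake are the urine half of the opioid-abstinence objective in inducted participants and the urine half of exploratory objective 5 in everyone enrolled. In the second, the people without urine are largely those who failed the primary outcome, and the plan expects more of them under SP than under RP.

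**Working it through.** **Planned numbers.** The design matrix (SAP Figure 1) has 5 + 4 + 3 + 2 + 1 + 0 = 15 RP cells out of 30, at 15 participants per cell. RP = 15 × 15 = 225 and SP = 15 × 15 = 225, total 450. This agrees with the plan.

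**Induction failures without scheduled post-induction urine.** SAP 12.0 assumes success of 0.55 in SP and 0.70 in RP.

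- SP: 225 × (1 − 0.55) = 101.25
- RP: 225 × (1 − 0.70) = 67.5
- Total: 168.75, and 168.75 / 450 = 37.5%

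This is an upper figure, because Protocol 10.5.5 lets failures receive study XR-NTX up to Week 8, which would trigger a screen. The documents give no rate for this. If 10% to 30% of failures were injected later (assumption), the share of all enrolled with none would be 37.5% × 0.90 = 33.75% down to 37.5% × 0.70 = 26.25%.

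**Inducted participants.** Expected number: 225 × 0.55 + 225 × 0.70 = 123.75 + 157.5 = 281.25. Let u be the share receiving the second injection. The documents give no value, so take 50% to 90% (assumption). Those without a Week 4 urine number 281.25 × (1 − u), which is about 141 at u = 50% and 28 at u = 90%.

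**Coverage of everyone enrolled at Week 4**, with the same u in both procedures and no late injections:

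- SP: 0.55 × u = 27.5% to 49.5%
- RP: 0.70 × u = 35% to 63%
- Gap: 0.15 × u = 7.5 to 13.5 percentage points

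So even with equal uptake, coverage differs by procedure because it follows the primary outcome.

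**Between-procedure bias in inducted participants.** Let a be the positive rate among those injected and b the rate among those not injected, each the same in both procedures. True positivity is u·a + (1 − u)·b, while the urines collected show a. The true RP minus SP difference that stays hidden is (u_SP − u_RP) × (b − a).

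- Uptake 70% SP and 60% RP, a = 10%, b = 60%: SP 0.7 × 0.10 + 0.3 × 0.60 = 25%; RP 0.6 × 0.10 + 0.4 × 0.60 = 30%; both appear as 10%. Hidden difference +5 points.
- The same uptake with b from 40% to 80%: 0.10 × 0.30 = 3 points to 0.10 × 0.70 = 7 points.
- Equal uptake: 0.
- Uptake reversed (60% SP, 70% RP), b = 60%: −5 points.

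None of these uptake or positivity values comes from the documents. The example shows that the rule can hide a difference, not that it does.

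**The case against.** The strongest reply is that the injection wording only fixes the order of procedures. Footnote 3 is shared with the pregnancy test, Protocol 12.2.6 asks for urine before self-report and before medication in most cases, and Protocol 10.5.7 keeps participants who stop medication on the same assessment schedule. SAP 8.4 and Protocol Table 3 name the visits without mentioning an injection. This reading is possible, and no sentence says that someone who attends but is not injected gives no urine. It does not settle the matter: SAP 2.2.2 leaves UDS off the visit list and gives the injection as its only trigger, and Protocol 10.5 says much the same. A site following those texts would not collect it.

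Several stronger readings are tempting, and the documents do not support them:

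- *No urine exists outside injections.* SAP 2.2.2 lists a baseline screen and allows inpatient screens to be abstracted from records. Late injections bring a screen, and participants who stop keep their earlier ones.
- *Induction failures are a gap in the opioid-abstinence objective.* SAP 8.4 restricts that objective to the Inducted Population. Protocol 16.3.2 does speak more broadly of analysing post-injection secondary outcomes in all enrolled as well, but the failures fall clearly only within exploratory objective 5.
- *The objectives cannot be answered.* Timeline Followback is the leading opioid-use measure in Protocol Table 3 and SAP Table 5, with urine as confirmation when available, and use is framed as use on study medication. Self-report is also collected from failures at Weeks 4 and 8. What is lost is urine confirmation.
- *A finding of comparable opioid use is built in.* The documents expect comparable retention. Protocol 10.5.6 puts full blockade at 5 weeks after an injection and counts relapse only from day 35, so an inducted participant who declines at Day 28 is still covered. The relapse mechanism bears more on Week 8 than on Week 4.

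Protocol 16.9 also says that sensitivity analyses will be considered for selected secondary outcomes. It does not say which outcomes or how, and SAP 8.7 deals only with the primary outcome.

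**Conclusion.** The concern holds as an unreconciled collection rule with a missing-data consequence for secondary and exploratory urine outcomes. Followed as written, up to about 101 of 225 SP and 68 of 225 RP participants (37.5% overall) have no scheduled post-induction urine, and inducted participants have none after their last injection. These counts rest on the planned success rates and on no late injections. The missingness is related to the outcome because relapse can stop injections, and for comparisons of everyone enrolled it is expected to differ by procedure.

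The direction and size of any between-procedure bias in the Inducted Population are unknown. The bias is zero if injection uptake and positivity are equal across procedures. A reader might infer a hidden difference of several points against RP, but that needs unequal uptake, which the documents neither state nor expect. The primary outcome is unaffected.

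**What to change.** Reconcile SAP 2.2.2, Protocol Table 7 footnote 3 and Protocol 10.5 with Protocol Table 3, SAP Table 5, SAP 8.4 and exploratory objective 5. State that UDS is collected at the Week 4 and Week 8 visits from every attending participant, including induction failures, whether or not XR-NTX is given. In Table 7 this means giving UDS its own footnote at those two visits. The cost is a minor amendment and one extra on-site urine cup per such visit, with no new visit.

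The SAP Table 55 shell already carries counts for 190 SP and 225 RP participants, so many visits may be past. For visits where urine was taken only before injections, change wording alone:

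- report the UDS proportion with its denominator, labelled *among participants receiving the injection*;
- do not interpret it as a between-procedure comparison of abstinence;
- limit the urine part of exploratory objective 5 to participants with a scheduled screen;
- state how urine missing because no injection was given will be handled.

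This costs SAP text only, and self-report then carries the comparison of opioid and other drug use.
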